- Have previously participated in this same study.
- Be a user of contact lenses and can not suspend their use during the study.
- That they can not follow the lifestyle considerations described in section 6.2.2
- Having started the use of hormonal contraceptives or IUD, 30 days prior to inclusion in the present study.
- Having a history of any chronic-degenerative disease.
- Present inflammatory or infectious disease, active at the time of admission to the study.
- Present injuries or unresolved traumas at the time of entering the study.
- Having the antecedent of any type of eye surgery.
- Having undergone surgical procedures, not ophthalmological, in the last 3 months.

Test product, dose and route of administration:

- PRO-179. Travoprost 0.004%. Ophthalmic solution. Sophia Laboratories, S.A. of C.V.
- Dosage: 1 drop at night.
- Route of administration: Ophthalmic.

Reference product, dose and route of administration:

- Travatan®. Travoprost 0.004%. Ophthalmic solution. Alcon Laboratories, Inc.
- Dosage: 1 drop at night. Both eyes.
- Route of administration: Ophthalmic.

Treatment duration:

10 days.

Duration of subject in the study:

15 to 22 days.

Evaluation criteria:

Primary outcome variables:

- Incidence of adverse events (AD) (Evaluation Time: day 5, 11 and 14).
- Ocular Comfort Index Score (ICO) (TE: day 11).

Secondary outcome variables:

- Changes in visual ability (TE: day 5 and 11).
- Changes in corneal and conjunctival staining with lysine green (TE: day 5 and 11).

- Changes in corneal and conjunctival staining with fluorescein (TE: day 5 and 11).
- Changes or conjunctival hyperemia (TE: day 5 and 11).
- Incidence of chemosis (TE: day 5 and 11).
- Incidence of alterations in the results of laboratory tests (TE: day 11).
- Incidence of alterations in heart rate (HR) (TE: day 5 and 11).
- Incidence of alterations in the respiratory frequency (RR) (TE: day 5 and 11).
- Incidence of alterations in systemic blood pressure (SBP) (TE: day 5 and 11)).

[figure not shown]
Exploratory outcome variables:

- Changes in intraocular pressure (TE: day 5 and 11).

Statistical methodology:

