- Compare the safety of PRO-179 with Travatan® by the incidence of chemosis during visits.
- Compare the safety of PRO-179 with Travatan® by means of the incidence of alterations in the results of the laboratory tests on day 11.

- Compare the safety of PRO-179 with Travatan® through the incidence of changes in HR during visits.
- Compare the safety of PRO-179 with Travatan® by means of the incidence of RF alterations during visits.
- Compare the safety of PRO-179 with Travatan® by the incidence of changes in SAD during visits.

5.5.3 Exploratory objectives.

- Compare changes in intraocular pressure during visits.

5.5.4 Hypothesis.

H0 The ophthalmic solution PRO-179 presents a profile of safety and tolerability similar to Travatan® in healthy subjects.

Ha The ophthalmic solution PRO-179 presents a different safety and tolerability profile Travatan® in healthy subjects.

5.6 Design and plan of the study.

Clinical trial, phase I, controlled, of parallel groups, double blind with randomization.

5.6.1 Discussion of the study design.

The design of the study (clinical trial) is considered the highest standard of data quality when looking to explore the effect of an intervention. The phase of pharmacological development (phase I) corresponds to the objective of the study which is to assess safety and tolerability, so that the intervention time is short and the sample size required is less than that of a clinical efficacy trial. The presence of parallel groups allows the comparison between the intervention groups on the outcome variables. Blinding and randomisation allow to reduce biases that are incurred with other designs, eg. selection bias, evaluation bias, among others.

The comparator, Travatan®, has a known safety profile and shares the same active principles in the same concentrations as PRO-179, which is why it was chosen as the best option to compare.

5.6.2 Justification of the posology.

The chosen dosage is one drop every 24 hours at night, this is the indicated and approved dosage for the reference medicine. Clinical studies demonstrate the sufficiency of 1 drop every 24 hours; likewise, they have shown that the administration at night presents less IOP fluctuations during 24 hours, unlike the morning application. [38]

For this phase I study, we do not consider it necessary to expose the research subjects to dosage rates higher than those recommended, since it is not justifiable.

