The return will be made by the research center when the sponsor indicates it. Prior to the return, the research center must make a count of the assigned medication and the remaining medication, with the aim of creating an inventory which serves for the final filling of the medication return form.

6.4 Delay variables.

6.4.1 Security variables.

6.4.1.1 Primary outcome variables.

- Incidence of adverse events.

6.4.1.2 Variables of primary outcome of tolerability.

- ICO score.

6.4.1.3 Secondary outcome variables.

- Changes in visual ability.
- Changes in corneal and conjunctival staining with lysine green.
- Changes in corneal and conjunctival staining with fluorescein.
- Changes conjunctival hyperemia.
- Incidence of chemosis.
- Incidence of alterations in the results of laboratory tests.
- Incidence of alterations in the FC.
- Incidence of alterations in the RF.
- Incidence of alterations in the TAS.

6.4.2 Exploratory variables.

- Changes in IOP.

6.4.3 Methods and scales to be used for the measurement of the variables.

Variable	Kind	Unit (Symbol)	Method of measurement	Normal value	Evaluation time	Statistical test
Primary						
Adverse events	Discreet Categorical rating	Number of cases (n) Present/absent	Count Observation	0 Absent	VB, V1, VF y LLS	Mann-Whitney U χ^2 o Fisher's exact
ICO score	Discreet	Points	Questionnaire	NA	VB, VF	Mann-Whitney U
Secondary						
Visual ability	Discreet	Fraction	Snellen Primer	1	VB, V1 y VF	Mann-Whitney U
Corneal and conjunctival staining with fluorescein	Ordinal	Degrees	Direct observation with slit lamp and cobalt blue filter, Oxford scale graduation	0	VB, V1 y VF	χ^2 or Fisher's exact

Variable	Kind	Unit (Symbol)	Method of measurement	Normal value	Evaluation time	Statistical test
Corneal and conjunctival staining with lysamine green	Ordinal	degrees	Direct observation with slit lamp, Oxford scale graduation	0	VB, V1 y VF	χ^2 or Fisher's exact
Conjunctival hyperemia	Ordinal	Normal / Very Light / Mild / Moderate / Severe	Direct observation. Classification of Efron.	Normal	VB, V1 y VF	χ^2 or Fisher's exact
Chemosis	Categorical rating	Present / absent		Absent	VB, V1 y VF	χ^2 or Fisher's exact
FC	Discreet	eats per minute (l / m)	Auscultation with stethoscope	60 to 100	VB, V1 y VF	Mann-Whitney U
FR	Discreet	Breaths per minute (r / m)	Auscultation with stethoscope	12 to 24	VB, V1 y VF	Mann-Whitney U
TAS	Discreet	Millimeters of mercury (mmHg)	Measurement with sphygmomanometer	90-120/ 60-80	VB, V1 y VF	Mann-Whitney U

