A drop of topical anesthetic will be instilled in the conjunctival cul-de-sac, then a second drop will be applied to the tip of the fluorescein strip and it will be allowed to slide towards the bottom of the sac. It is essential to quickly evaluate the staining, in sequence, first in the OD and then the OS, so that the observed patterns are equally bright. This valuation will be done with the cobalt blue filter. [61] See annex Scale of Oxford.

6.4.3.5 Presence of adverse events.

The management of the EAs will be done according to what is described in the Adverse Events section.

The PI will register in the corresponding section of the CRF the EAs that come to present the subjects of the study in addition to referring it in the clinical file.

6.4.3.6 Intraocular pressure.

Tonometry is the objective measure of IOP, based primarily on the force required to flatten the cornea or the degree of corneal indentation produced by a fixed force. Goldman's tonometry is based on the Imbert-Fick principle. [57] The tonometry will be performed, after instillation of a drop of topical anesthetic (tetracaine 0.5%), with fluorescein and the use of the cobalt blue filter (after evaluation of the corneal surface staining). There will be 3 shots, which will be recorded in the clinical file and the average will be registered in the CRF.

6.4.3.7 Vital signs.

The vital signs to be evaluated (FC, FR and TAS) can be measured by an assistant duly indicated in the organization of the center and the delegation of responsibilities, the technique to be used for the FC and FR will be with the count of repetitions in one minute by direct auscultation with stethoscope.

The SBP should be measured with 5 minutes of previous rest, in the left arm. The instrument can be manual or automatic according to the PI. It is necessary that all measurements are equal in circumstances. The PI will register in the note and the CRF.

6.4.3.8 Laboratory tests.

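### Vital-sign outcomes are defined as incidences of alterations, but Table 3 assigns them only a rank test on the measured values and defines no alteration

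*Combined protocol and SAP*

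**What the plan says.** **Outcome definitions.** The synopsis lists "Incidence of alterations in heart rate (HR) (TE: day 5 and 11") among the secondary outcomes, with parallel entries for respiratory rate and blood pressure. Section 6.4.1.3 repeats them: "Incidence of alterations in the FC", "Incidence of alterations in the RF" and "Incidence of alterations in the TAS". Section 5.5.2 frames the heart-rate objective as a comparison of the products "through the incidence of changes in HR during visits"; it names no days, which only the synopsis gives.

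**Operational definitions.** In Table 3 (6.4.3), all three signs are classed as discrete and measured per minute or in mmHg. The printed normal values are 60 to 100 (heart rate), 12 to 24 (respiratory rate) and 90-120/60-80 (blood pressure). The only test assigned to each is Mann-Whitney U. Blood pressure is a single row, with method "Measurement with sphygmomanometer".

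**Measurement.** Section 6.4.3.7 describes technique, for example "The SBP should be measured with 5 minutes of previous rest, in the left arm". SBP here is the plan's abbreviation for systemic, not systolic, blood pressure. The section does not define an alteration.

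**General rule.** Section 8.3.1 refers to Table 3 for the variables and says that qualitative variables are shown as frequencies and percentages and compared by chi-square or Fisher's exact test.

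**The concern.** An incidence is a proportion of subjects who meet a criterion. A rank test on the measured values compares two distributions, which is a different question. It need not respond when more subjects in one arm go out of range in both directions, and it can respond to a shift that stays inside the normal range.

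Safety is the purpose of this trial. If the criterion for an alteration is not fixed beforehand, any incidence reported for these outcomes will rest on a rule chosen after the data exist. The open choices are which limits apply, whether clinical judgement enters, how the two visits are handled, and whether systolic and diastolic pressure are counted separately.

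**Working it through.** **1. Definition against assigned test**

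| Outcome | Worded in 6.4.1.3 as | Table 3 form | Table 3 test |
|---|---|---|---|
| Adverse events | incidence | count and present/absent | Mann-Whitney U and chi-square/Fisher |
| Chemosis | incidence | present/absent | chi-square/Fisher |
| Heart rate, respiratory rate, blood pressure | incidence | measured value | Mann-Whitney U only |
| Laboratory tests (15 rows) | incidence | measured value | Mann-Whitney U only |

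Section 6.4.1.3 uses the word changes for visual ability, staining and hyperemia, so incidence appears to be a deliberate distinction. Where Table 3 intends an incidence comparison (adverse events, chemosis), it says so. Three of nine secondary outcomes are vital signs with the mismatch; the laboratory outcome makes four.

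**2. Blood pressure.** A pair of numbers cannot be ranked as one value, so the row cannot be run as printed without deciding whether it means two tests or one.

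**3. Do the two analyses differ in practice?** The plan gives no figure to reproduce here. The means and SDs below are assumptions; n = 12 per arm and the limits 60-100 are the plan's. Values are rounded to whole beats.

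Share out of range = Φ((59.5 − μ)/σ) + 1 − Φ((100.5 − μ)/σ):

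- μ 76, σ 8: Φ(−2.06) + Φ(−3.06) = 0.020 + 0.001 = 2.1%
- μ 76, σ 16: Φ(−1.03) + Φ(−1.53) = 0.151 + 0.063 = 21.4%
- μ 76, σ 6: Φ(−2.75) + Φ(−4.08) = 0.3%
- μ 83, σ 6: Φ(−3.92) + Φ(−2.92) = 0.2%

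Rejection rates at 0.05, from 20,000 simulated trials per case and repeated with different seeds:

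| Case | Out of range | Mann-Whitney U | Fisher on incidence |
|---|---|---|---|
| (a) 76, SD 8 v 76, SD 16 | 2% v 21% | 5.3-5.5% | about 7% |
| (b) 76, SD 6 v 83, SD 6 | 0.3% v 0.2% | 74-75% | 0% |

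A second set of assumptions (4,000 trials, reference arm mean 80, SD 8) gives the same pattern. With the test arm at mean 80, SD 24, 1% v 39% are out of range; Mann-Whitney rejects in 6% and Fisher in 48%. With the test arm at mean 90, SD 8, 1% v 9% are out of range; Mann-Whitney rejects in 80% and Fisher in under 1%.

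**4. What the incidence analysis can deliver at 12 per arm** (two-sided Fisher)

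- 4/12 v 0/12: p = 2·C(12,4)/C(24,4) = 2·495/10,626 = 0.093
- 5/12 v 0/12: p = 2·C(12,5)/C(24,5) = 2·792/42,504 = 0.037
- 0/12 altered: exact two-sided 95% upper bound = 1 − 0.025^(1/12) = 26.5%

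**5. Ordinary variation.** Assume healthy systolic pressure with mean 110-112, SD 8-9 and between-visit correlation 0.6, under a multivariate normal simulated with 400,000 draws and rounded to whole mmHg. The share outside 90-120 at either of two visits is then about 16-28%. Counting only subjects inside the limits at baseline, and one visit at a time, lowers it to about 7-12%.

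**The case against.** The strongest reply is that this is under-specification and not an omission. The values are collected at Visit 1 and the final visit, Table 3 prints a normal range for each sign, and both the synopsis and 8.3.1 contain a general chi-square/Fisher rule for qualitative variables. An analyst could therefore produce the incidence. That stands. A reader might infer that these outcomes are never analysed as stated, or that the trial cannot report them; the documents do not support either. What the reply leaves open is that Table 3 does not class the signs as qualitative, and no passage turns a reading into an alteration.

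A reader might also infer that abnormal vital signs would go unnoticed. They would not: section 9.2.1 detects adverse events by questioning, diary review and examination, names systemic arterial hypertension as an example, and adverse-event incidence is a primary outcome with chi-square/Fisher assigned. That route covers events judged adverse, not every out-of-range reading.

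The single blood-pressure row may be shorthand for two analyses. That is possible, but the plan should say so.

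Finally, the simulation rests on assumed values, and case (a) posits a doubled SD between two products with the same active ingredient and concentration. Fisher has little power there, and in case (b) Mann-Whitney detects a 7-beat shift that the incidence misses. This is a good reason to keep Mann-Whitney, but not to let it stand in for the stated outcome.

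**Conclusion.** The point holds as a mismatch between the stated outcome and the assigned analysis. It covers the three vital signs and, in the same way, the laboratory outcome: four of nine secondary outcomes. The assigned test does not estimate the incidence. It can be non-significant when out-of-range counts differ, or significant when almost nobody is out of range. The text comparison needs no assumption; the rejection rates depend on the assumed means and SDs and show only that the two analyses can diverge.

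A reader might infer that the trial's safety conclusion is affected. It is not: the rule in 8.3.1 for declaring the product safe and tolerable uses the primary outcomes only. The consequence is limited to secondary safety reporting, where a correction is worthwhile because it is nearly free. Nor does correcting it add useful power at this sample size. The gain is a pre-specified estimate of the quantity that the plan names.

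**What to change.** In Table 3 and 8.3.1:

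- Add a present/absent row per subject for heart rate, respiratory rate, systolic pressure and diastolic pressure.
- Pre-specify an alteration as an on-treatment value outside the Table 3 limits in a subject whose baseline value was inside them. The baseline condition is needed because 6.2.1.1 asks for normal vital signs at entry without citing the Table 3 limits. State which reading is the baseline, since 6.4.4 allows screening values to serve.
- Tabulate at Visit 1 and at the final visit separately.
- Compare arms by Fisher's exact test, with the difference in proportions and an exact 95% confidence interval.
- Keep Mann-Whitney U on the measured values as a supporting analysis, run separately for systolic and diastolic pressure.
- Apply the same correction to the laboratory outcome once the Table 3 normal values and the laboratory ranges with the ±20% margin in 6.4.3.8 have been reconciled.

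The cost is a few lines of text and slightly more tabulation; no new data, visits or subjects are needed. Power stays low, and some out-of-range readings will be ordinary variation, so the results should be read as estimates with intervals and not as pass/fail tests.

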The closing of the center will be carried out once the last visit of the last included subject previously agreed between the sponsor and the PI has been made. The closing process will be according to the normal procedures of the sponsor's internal operations and must have the disposition and participation of the PI and whoever he designates.

It is the sponsor's prerogative to prematurely close a study center, it must inform the PI the reasons for the closure. These can be, but do not exclude:

- a) Lower recruitment to the projected.
- b) Deviations greater than the protocol, which at the sponsor's discretion merit closing the center.
- c) Recidivism of deviations to the protocol, which at the sponsor's discretion merit closing the center.
- d) Early termination of the study.

6.2 Study population.

6.2.1 Selection criteria.

6.2.1.1 *Inclusion criteria.*

- Be clinically healthy.
- Have the ability to give their signed informed consent and show willingness to comply with the study procedures
- Have an age between 18 to 45 years.
- Indistinct sex.
- Women should ensure the continued use of a hormonal contraceptive method or intrauterine device (IUD) during the study period.
- Present blood tests: within normal parameters or with a range of \pm 20% as long as the subject is clinically healthy.
 - o Blood count (BH): Hemoglobin, erythrocytes, hematocrit, total leukocytes, platelets, mean corpuscular volume and mean corpuscular hemoglobin.
 - o Blood chemistry of three elements (QS): Glucose, urea and creatinine.
 - o Liver function tests (PFH): TGO, TGP, total bilirubin, direct and indirect.
- Present visual ability 20/30 or better in both eyes.
- Present vital signs within normal parameters.
- Present intraocular pressure \geq 10 and \leq 21 mmHg.

6.2.1.2 *Exclusion criteria.*

6.2.1.2.1 General criteria.

- Be a user of ophthalmic topical products of any kind.
- Be a user of medicines, or herbal products, by any other route of administration, with the exception of hormonal contraceptives in the case of women.
- In case of being a woman, being pregnant or breastfeeding.

- Have participated in clinical research studies 90 days prior to inclusion in the present study.
- Have previously participated in this same study.
- Be a user of contact lenses and can not suspend their use during the study.
- That they can not follow the lifestyle considerations described in numeral 6.2.2

6.2.1.2.2. Medical and therapeutic criteria.

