Erythrocytes	Continuous	Thousands per microliter (Mil / dL)	Laboratory analysis	4.0- 6.3	VB y VF	Mann-Whitney U
Hemoglobin	Continuous	Grams over deciliter (g / dL)	Laboratory analysis	11.0-16.0	VB y VF	Mann-Whitney U
Hematocrit	Continuous	Percentaje (%)	Laboratory analysis	36-51	VB y VF	Mann-Whitney U
VGM	Continuous	Femto liters (fL)	Laboratory analysis	80-97	VB y VF	Mann-Whitney U
HCM	Continuous	Picograms (pg)	Laboratory analysis	25-32	VB y VF	Mann-Whitney U
Leukocytes	Continuous	Thousands per liter units (Mil / uL)	Laboratory analysis	4.0-11.0	VB y VF	Mann-Whitney U
Platelets	Continuous	Thousands per liter units (Mil / uL)	Laboratory analysis	150-400	VB y VF	Mann-Whitney U
Glucose	Continuous	Milligrams over deciliter (mg / dL)	Laboratory analysis	70-100	VB y VF	Mann-Whitney U
Urea	Continuous	Milligrams over deciliter (mg / dL)	Laboratory analysis	10-50	VB y VF	Mann-Whitney U

Variable	Kind	Unit (Symbol)	Method of measurement	Normal value	Evaluation time	Statistical test
Creatinine	Continuous	Milligrams over deciliter (mg / dL)	Laboratory analysis	0.6-1.1	VB y VF	Mann-Whitney U
Glutamic pyruvic transaminase	Continuous	Units over liter (U / L)	Laboratory analysis	0-31	VB y VF	Mann-Whitney U
Oxalacetic glutamic transaminase	Continuous	Units over liter (U / L)	Laboratory analysis	0-32	VB y VF	Mann-Whitney U
Total bilirubin	Continuous	Milligrams over deciliter (mg / dL)	Laboratory analysis	0-1.1	VB y VF	Mann-Whitney U
Direct bilirubin	Continuous	Milligrams over deciliter (mg / dL)	Laboratory analysis	0.0-0.3	VB y VF	Mann-Whitney U
Indirect Bilirubin	Continuous	Milligrams over deciliter (mg / dL)	Laboratory analysis	0.0-0.8	VB y VF	Mann-Whitney U
Exploratoria						
Presión intraocular	Continuous	Millimeters of mercury (mmHg)	Goldmann Tonometry	10 to 21	VB, V1 y VF	Mann-Whitney U

Table 3. Table of operational definitions of variables.

The following describes the methods and scales that will be used to measure the variables, which are in strict alphabetical order:

6.4.3.1 Visual capacity.

Visual acuity (VA) is a test of visual function. Spatial visual acuity is the ability to distinguish separate elements of an object and identify them as a whole. It is quantified as the minimum separation angle (located at the nodal point of the eye) between two objects that allows perceiving them as separate objects.

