The designated personnel will perform the extraction of the blood sample, through venipuncture. The vein will be chosen at the discretion of the personnel in charge and will perform asepsis of the skin of the area to be punctured prior to the procedure. It will generate the order of the studies of BH, QS and PFH, to be carried out by the clinical laboratory designated by the sponsor. The clinical laboratory will deliver to the the results for its assessment and registration. The normal parameters to be considered will be the ranges established by the laboratory, with a lower and superior margin of 20% in a clinically healthy subject, at the discretion of the PI.

6.4.4 Measurement time.

The measurements of the variables of primary and secondary outcome, as well as the activities contemplated in the protocol, will be carried out and evaluated for each visit, according to the following:

Basal Visit / Day 1.

Some of these measurements will be taken at the screening visit to complete the eligibility criteria, at the discretion of the PI, they may be taken to complete the baseline visit data.

1. 1. Eye comfort index.
2. 2. Visual ability
3. 3. Vital signs
4. 4. Evaluation of ocular surface.
5. to. It includes stains.
6. 5. Intraocular pressure.
7. 6. Comprehensive ophthalmological evaluation.
8. 7. Evaluation of adverse events.
9. 8. Evaluation of results of laboratory tests.

Visit 1 / Day 5.

1. It can be done in a period \pm 1 days in relation to the 4th day of application.
2. 1. Visual ability
3. 2. Intraocular pressure.
4. 3. Evaluation of ocular surface.
5. to. It includes stains.
6. 4. Comprehensive ophthalmological evaluation.
7. 5. Vital signs
8. 6. Evaluation of adverse events.

Final Visit / Day 11.

1. It can be done in a period + 1 day in relation to day 11, not before day 11 since the 10 days of application would not be fulfilled.
2. 1. Visual ability
3. 2. Intraocular pressure.
4. 3. Eye comfort index.
5. 4. Evaluation of ocular surface.
6. to. It includes stains.
7. 5. Comprehensive ophthalmological evaluation.
8. 6. Vital signs
9. 7. Evaluation of adverse events.

Security call / Day 14.

1. It can be done in a period \pm 1 day in relation to the 14th day of the start of application.
2. 1. Ask about the presence of an adverse event.
3. 2. Evaluation of results of laboratory tests.

6.5 Timeline and study diagram.

Procedures	Scrutiny	VB	V1	VF	LIS
	D 1 - X ^a	D 1	D 5 ± 1	D 11 a + 1	D 14 ± 1
CI Signature	X				
Clinic history	X				

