- Delivery of IP: Refers to the delivery of the product under investigation to the patient of the study, by the research center. It will be done according to section 6.3.4.1 Delivery and reception.
- Delivery of the subject's diary: It refers to the delivery by the PI to the subject of the instrument: the subject's diary. The assigned personnel will perform a training on the subject, on the filling of the instrument.
- Adverse events: see 6.4.3.5 Presence of adverse events.
- Evaluation of concomitant medications: Ver **¡Error! No se encuentra el origen de la referencia.**

6.5.1.3 Visit 1.

- Return / evaluation of the subject's diary: refers to the submission of the subject's diary to the PI by the subject. The PI will review the journal to assess its correct filling, and the registration of the applications.
- Adherence evaluation: refers to the assessment performed by the PI according to the section Procedure to monitor adherence.
- Delivery of the subject's diary: see Basal visit.
- Adverse events: see 6.4.3.5 Presence of adverse events.
- Vital signs: see 6.4.3.7 Vital signs.
- Visual capacity: see 6.4.3.1 Visual capacity.
- Integrity of the ocular surface: see 6.4.3.4 Integrity of ocular surface:
- Intraocular pressure: see 6.4.3.6 Intraocular pressure.
- Evaluation of concomitant medications: See 6.5.1.1
- Continuity assessment of the subject: refers to the determination by the PI and desire of the subject to continue with their participation in the study.

6.5.1.4 Final visit.

- Return of the IP: refers to the return of the IP by the subject to the non-blind staff of the center.
- Return / evaluation of the subject's diary: see Visit 1.
- Adherence evaluation: refers to the assessment made by the PI according to section 6.3.2.1 Procedure to monitor adherence.
- Adverse events: see 6.4.3.5 Presence of adverse events.
- Urine pregnancy test: see Screening visit.
- Vital signs: see 6.4.3.7 Vital signs.
- Visual capacity: see 6.4.3.1 Visual capacity.
- Comprehensive ophthalmological evaluation: see 6.4.3.2 Comprehensive ophthalmological evaluation.
- Integrity of the ocular surface: see 6.4.3.4 Integrity of ocular surface:
- Intraocular pressure: see 6.4.3.6 Intraocular pressure.
- Sampling of laboratory samples: see 6.4.3.8 Laboratory tests.
- Eye comfort index: see 6.4.3.3 Eye comfort index.

- Evaluation of concomitant medications: See **iError! No se encuentra el origen de la referencia.**

6.5.1.5 Security call.

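### The day-11 incidence of laboratory alterations has no single definition of an alteration, and Table 3 assigns it no test of incidence

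*Combined protocol and SAP*

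**What the plan says.** The synopsis lists as a secondary outcome "Incidence of alterations in the results of laboratory tests (TE: day 11"). Section 5.5.2 sets the matching objective: to compare the products "by means of the incidence of alterations in the results of the laboratory tests on day 11". Section 6.4.1.3 repeats the outcome.

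Three places bear on what counts as normal or altered:

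- **6.2.1.1 (eligibility)** admits blood results in the normal range or within ±20% of it, "as long as the subject is clinically healthy".
- **6.4.3.8 (laboratory method)** says: "The normal parameters to be considered will be the ranges established by the laboratory, with a lower and superior margin of 20" per cent, "in a clinically healthy subject, at the discretion of the PI". It does not restrict this to screening. The final-visit list in 6.5.1.4 refers to it: "Sampling of laboratory samples: see 6.4.3.8 Laboratory tests".
- **Table 3 (6.4.3, operational definitions)** gives fixed normal values with no margin, classes all 15 analytes as continuous, and assigns one test. Two of its rows read "Hemoglobin Continuous Grams over deciliter (g / dL) Laboratory analysis 11.0-16.0 VB y VF Mann-Whitney U" and "Creatinine Continuous Milligrams over deciliter (mg / dL) Laboratory analysis 0.6-1.1 VB y VF Mann-Whitney U".

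Section 8.3.1 adds general rules. Qualitative variables go into 2x2 tables, with chi-square or Fisher's exact between groups and McNemar within groups. Quantitative variables get Mann-Whitney between groups and Wilcoxon within groups.

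**The concern.** An incidence needs a rule that turns each subject's day-11 result into yes or no. The plan offers two candidate ranges and does not say which one governs the outcome. One of them also depends on the investigator's discretion. Neither is linked to the subject's screening value, although eligibility deliberately admits some people whose values are already outside the range.

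Separately, the test that Table 3 assigns compares distributions of raw values. It does not compare the number of subjects with an alteration, so it does not answer the objective in 5.5.2.

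At stake is reproducibility. Two competent analysts could report different laboratory incidences from the same data. A pre-existing deviation could be counted as an event, and a new one might not be.

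**Working it through.** The plan states no figure for this outcome, so there is none to reproduce. The inputs are the Table 3 ranges, the 20% margin in 6.4.3.8, and 12 subjects per group from 6.6.

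**Step 1. Widened ranges.** The text does not say what the 20% is a percentage of, so two readings are shown. Both assume that the laboratory's own limits equal Table 3.

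- Reading A: 0.8 × lower limit to 1.2 × upper limit.
- Reading B: 0.2 × (upper − lower) added at each end.

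| Analyte | Table 3 | Reading A | Reading B |
|---|---|---|---|
| Hemoglobin, g/dL | 11.0–16.0 | 8.8–19.2 | 10.0–17.0 |
| Platelets, thousands | 150–400 | 120–480 | 100–450 |
| Creatinine, mg/dL | 0.6–1.1 | 0.48–1.32 | 0.5–1.2 |
| TGP, U/L | 0–31 | up to 37.2 | up to 37.2 |

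**Step 2. Results that change class.**

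- TGP 36 U/L at screening and at day 11: 31 < 36 < 37.2. It is eligible under the margin. On day 11 it is an alteration under Table 3 although nothing changed, and it may be normal under 6.4.3.8. The two readings agree because the lower limit is zero.
- Hemoglobin 9 g/dL on day 11: below 11.0, so abnormal under Table 3. Under 6.4.3.8 it may be normal in reading A (9 > 8.8) and is abnormal in reading B (9 < 10.0).

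**Step 3. Effect on the count.** Assume that each Table 3 range is the central 95% of a normal distribution, so SD = (upper − lower)/3.92. For hemoglobin the mean is 13.5 and the SD is 5/3.92 = 1.28. The reading A limits lie at −3.68 and +4.47 SD, so the share flagged falls from 5% to about 0.01%. Across the 10 analytes with a non-zero lower limit, the share under reading A falls from 5% to between about 0% (VGM) and 1.7% (urea).

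**Step 4. Mann-Whitney against an incidence.** Two simulations of 4,000 runs each used assumed values at 12 v 12:

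- Three of 12 subjects in one arm have grossly raised transaminase (60–120); everyone else follows mean 20, SD 4. Mann-Whitney rejects in about 13% of runs.
- Both arms are effectively within range (means 15 and 20, SD 3), with essentially no abnormal values. Mann-Whitney rejects in about 96% of runs.

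The test responds to a shift in location, not to the number of abnormal subjects.

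**Step 5. What an incidence test could show.** For k v 0 at 12 v 12, the two-sided Fisher p-value is 2 × C(12,k)/C(24,k):

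- k = 2: 2 × 66/276 = 0.478
- k = 3: 2 × 220/2024 = 0.217
- k = 4: 2 × 495/10626 = 0.093
- k = 5: 2 × 792/42504 = 0.037

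At least 5 v 0 is needed for p≤0.05.

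**The case against.** Four replies have weight.

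- **Incidence can be tested under the plan.** A reader might infer that the plan cannot test incidence at all. That goes too far, because the 2x2 rule in 8.3.1 would cover a present/absent laboratory variable. What stands is that Table 3 creates no such variable for any analyte. For adverse events it lists both a count and a present/absent form, each with its own test.
- **Baseline is used somewhere.** The within-group Wilcoxon test in 8.3.1 is a paired comparison with the subject's own earlier value. It still does not define or count an alteration.
- **The margin may not reach day 11.** Table 3 may simply print the base ranges to which 6.4.3.8 adds a tolerance. The final-visit reference to 6.4.3.8 concerns sampling. The review of results at the safety call (6.5.1.5) points to the baseline visit, whose text states no margin. No sentence applies the margin to the outcome. But 6.4.3.8 is the only text on interpreting laboratory results, and it is not limited to screening, so the plan leaves the question open.
- **Fisher's test is no rescue.** At 3 v 0 it never reaches 0.05, while Mann-Whitney rejected in about 13% of the simulated runs. This is correct, and it means the case for change rests on the per-subject count.

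A reader might also infer that clear deteriorations must be recorded as normal. The documents do not support that. The margin is tied to a clinically healthy subject and left to the investigator's discretion, so a deterioration may be treated as normal, and the hemoglobin example holds under only one reading of the 20%.

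**Conclusion.** The point holds as two separate defects. First, there is no single definition of a day-11 alteration: 6.4.3.8 and Table 3 can classify the same value differently, and the difference is partly discretionary. Second, the only test that Table 3 assigns does not address the incidence objective. The two do not compound, because Mann-Whitney uses raw values and is unaffected by either range.

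The numerical examples assume that the laboratory's limits equal Table 3. The TGP example then holds under either reading of the margin. The shares in step 3 and the simulation results rest on the distributions assumed there.

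The consequence is limited. A reader might infer that the trial's safety conclusion is compromised, but 8.3.1 bases that conclusion on the primary outcomes, and laboratory alterations are secondary. The plan should be corrected because laboratory safety is a stated objective of a safety trial and the correction is cheap.

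**What to change.** Reconcile 6.4.3.8, Table 3 and 8.3.1:

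- State that the ±20% margin applies to eligibility only.
- Define a day-11 alteration as a value outside the laboratory's own unwidened range that was inside it at screening. Show values already outside at screening separately in the shift table, so that trivial movements are not counted as events.
- Report the number of subjects per arm with an alteration, with a screening-to-day-11 shift table. Use the Fisher's exact test already in 8.3.1, and keep Mann-Whitney on the values as supportive.
- Apply the same per-subject count to heart rate, respiratory rate and blood pressure. These are also named as incidences, but Table 3 assigns them only Mann-Whitney.

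The cost is wording in three sections and one added table; both blood samples are already scheduled. The downside is that more minor out-of-range values will be listed. The p-value will also rarely be informative at this sample size, so the report should rest on the counts and the shift table.
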